11.3.4 Rescue Therapy Use

11.3.4.1 Blood Transfusion

For a subject receiving RBC transfusion, the Time at Risk (time up to first RBC transfusion) will be calculated (in years) as:

$$(\text{First RBCtransfusion date} - \text{First dose date of study medication} + 1) / 365.25$$

For a subject not receiving transfusion, the Time at Risk (time until they get censored) is calculated as:

$$(\text{Date of last study medication} - \text{First dose date of study medication} + 1) / 365.25$$

The blood transfusion form of the eCRF in the cumulative visit will be used to derive the number of RBC packs. The number of RBC units is collected in this form. For transfusions where the number of units is not given but the volume transfused is given, the number of units will be estimated by dividing the volume transfused by 250 mL (for transfusion of packed cells) or by dividing the volume transfused by 500 mL (for transfusion of whole blood).

The total number of RBC units/packs during the treatment period is calculated for each subject by the sum of the transfused units between the Analysis Date of First Dose and up to the Analysis Date of Last Dose. The following 2 endpoints will be analyzed:

- Proportion of subjects who receive RBC transfusions. The proportion of subjects who received RBC transfusion will be compared between the 2 treatments using logistic regression model adjusting for baseline stratification factors.
- Number of RBC packs per patient-month exposure to study medication. The mean number of RBC packs will be compared between the 2 treatment groups using ANCOVA model with baseline hemoglobin as covariate and treatment and stratification factors as fixed effect.

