4.4 ADDITIONAL EVALUATION OF EFFICACY

The additional efficacy evaluations in this study are:

- **Hb Correction and Maintenance:**
 - Hemoglobin maintenance: Mean change from baseline in Hb averaged over 8 weeks of treatment at Weeks 28 to 36, without rescue therapy within 6 weeks prior to and during this 8-week evaluation period.
 - Hemoglobin long-term Maintenance: Mean change in Hb averaged over 8 weeks of treatment at Weeks 44-52 without rescue therapy within 6 weeks prior to and during this 8-week evaluation period.
 - Mean change from baseline in Hb averaged over the 96 to 104 weeks of treatment, without rescue therapy within 6 weeks prior to and during this 8-week evaluation period.
 - Change from baseline in Hb at each of the selected post-dosing time points.
 - Proportion of subjects with Hb ≥ 10 g/dL averaged over Weeks 28-36, without rescue therapy within 6 weeks prior to and during this 8-week evaluation period.
 - Proportion of subjects with mean Hb < 9 g/dL, 9- <10 , 10- <11 , 11- <12 , 12- <13 , ≥ 13 g/dL during Weeks 28-36
 - Proportion of patient exposure (PEY) with Hb < 9 g/dL, 9- <10 , 10- <11 , 11- <12 , 12- <13 , ≥ 13 g/dL during weeks 28 to 52
- **Hospitalizations:**
 - Time to first hospitalization (% of subjects) up to Week 52.
 - Time to first hospitalization or skilled nursing facility (% of subjects) up to Week 52
 - Number of days of hospitalizations per patient-exposure year (PEY).
 - Number of days of hospital or skilled nursing facility per PEY
 - Number of medical-facility free days (hospital, skilled nursing facility, emergency room, or overnight observation) per PEY
 - Number of days on treatment out of hospital and skilled nursing facility up to Week 52, 7 days after Last Dose.
- **Missed dialysis sessions up to Week 52**
 - Occurrence (number) of missed dialysis sessions
 - Proportion of subjects with missed dialysis sessions
 - Number of days of missed dialysis sessions per patient-exposure year (PEY)

- **Rescue Therapy Use up to Week 52:**
 - Proportion of subjects who receive RBC transfusions.
 - Number of RBC packs per patient-month exposure to study medication.
 - Roxadustat subjects: The proportion of subjects requiring ESA rescue therapy (ATC code: B03XA01)
- **Changes in Cholesterol Levels:**
 - Change at each of the protocol specified treatment time points in:
 - total cholesterol,
 - low-density lipoprotein (LDL)/high-density lipoprotein (HDL) ratio,
 - non-HDL cholesterol.

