11.3.4.2 ESA Usage as Rescue Therapy for roxadustat-treated Subjects

For roxadustat-treated subjects, ESA, as rescue therapy will be recorded in the ESA log of the eCRF. The total number of ESA-week dose per subject will be calculated.

For each entry that meets the criteria below the ESA-week will be calculated as follows:

- If drug is epoetin alfa, epoetin beta, or an epoetin biosimilar (ATC code: B03XA01), then $\text{ESA-Weeks} = (\text{stop date} - \text{start date} + 1) / 7$;
- If drug is darbepoetin SQ or IV dose (ATC code: B03XA02), then $\text{ESA-Weeks} = 2 \times (\text{stop date} - \text{start date} + 1) / 7$;
- If drug is Mircera IV or SQ dose (ATC code: B03XA03), then $\text{ESA-Weeks} = 4 \times (\text{stop date} - \text{start date} + 1) / 7$;
- If drug is peginesatide dose IV or SQ (ATC cod: B03XA04), then $\text{ESA-Weeks} = 4 \times (\text{stop date} - \text{start date} + 1) / 7$.

The total number of ESA-week during the treatment period is calculated for each subject by the sum of the ESA-week between the analysis date of First dose and the analysis date of Last dose.

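### SAP 4.4 limits the rescue-therapy endpoints to Week 52, but SAP 11.3.4 states no such limit and compares the proportion transfused by logistic regression with no exposure term

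*SAP*

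**What the plan says.** SAP 4.4 places three endpoints under the heading "Rescue Therapy Use up to Week 52": the proportion of subjects transfused, RBC packs per patient-month of exposure, and, in its words, "Roxadustat subjects: The proportion of subjects requiring ESA rescue therapy" (ATC code B03XA01).

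The analysis text reads differently.

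- **SAP 11.3.4.1, counting rule.** "The total number of RBC units/packs during the treatment period is calculated for each subject by the sum of the transfused units". Counting starts at the first dose and ends at the last. The section then names two endpoints to be analysed, the proportion transfused and packs per patient-month, and mentions Week 52 for neither.
- **SAP 11.3.4.1, model.** "The proportion of subjects who received RBC transfusion will be compared between the 2 treatments using logistic regression model adjusting for baseline stratification factors". There is no exposure or follow-up term.
- **SAP 11.3.4.2.** "The total number of ESA-week during the treatment period is calculated for each subject", again from first to last dose, over four ATC codes (B03XA01 to B03XA04). It gives no summary of the proportion needing ESA rescue.

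Protocol 7.3 lists the transfusion and ESA-rescue endpoints with no time window. SAP section 3 says treatment length varies by subject, may be under 52 weeks, and can extend to about 3 years after the last subject is randomized.

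**The concern.** A subject first transfused in the second year counts as an event if 11.3.4.1 is followed from first to last dose, and does not count under 4.4. Two programmers working from the same SAP could report different proportions. In an open-label trial, a window left open could be settled after results by arm are visible.

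The proportion transfused has a further weakness. A crude proportion counts every subject who stops early without a transfusion as untransfused, whatever the time at risk. If one arm stops treatment sooner, it looks better with no true difference. The longer the window, the more room there is for this. Unequal treatment length is possible here: under protocol 3.6.3.2 a second course of ESA rescue requires permanent discontinuation, and ESA rescue exists only in the roxadustat arm.

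**Working it through.** The plan states no transfusion rate, ESA-rescue rate, mean exposure or discontinuation rate, so there is no figure of its own to reproduce. Every rate below is an assumption. Week 52 is taken as 1 year.

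**Formula.** Let h be a constant yearly hazard of first transfusion, q a constant yearly hazard of discontinuation, and c the follow-up limit in years (capped at 1 for the Week 52 window). Then

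p(c) = h/(h+q) × [1 − exp(−(h+q)c)],

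averaged over the spread of planned treatment ends.

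**1. How far apart are the two readings?** With fixed duration T and no dropout, p(T) = 1 − (1 − p52)^T. For p52 = 10%, two years gives 1 − 0.81 = 19.0% (ratio 1.90) and three years gives 1 − 0.729 = 27.1% (ratio 2.71). The ranges are:

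| Scenario | Whole-period ÷ Week 52 proportion |
|---|---|
| Fixed 1.5 years, p52 3% to 20% | 1.42 to 1.49 |
| Fixed 2 years | 1.80 to 1.97 |
| Fixed 3 years | 2.44 to 2.91 |
| Ends spread over 0.5 to 2 years, q 0 to 0.4, 5% to 15% transfused by one year | 1.22 to 1.35 |
| Ends spread over 0.5 to 3 years, same q and rates | 1.44 to 1.79 |
| Ends spread over 0.5 to 4 years, same q and rates | 1.60 to 2.23 |

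Overall the ratio runs from about 1.2 to 2.9.

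**2. What happens to the odds ratio with no true difference?** Take h = 0.12 in both arms, treatment ends uniform over 1 to 4 years, and q = 0.30 in one arm against 0.20 in the other. Then k = h+q is 0.42 and 0.32.

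- Week 52: 0.2857 × (1 − 0.6570) = 9.8%, and 0.3750 × (1 − 0.7261) = 10.3%. Odds ratio 0.949.
- Whole period: p = (h/k) × [1 − (e^(−k) − e^(−4k))/(3k)]. This gives 0.2857 × (1 − 0.3735) = 17.9%, and 0.3750 × (1 − 0.4668) = 20.0%. Odds ratio 0.872.
- Share of the log-odds bias left by the Week 52 limit: ln 0.949 / ln 0.872 = 0.38.

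With equal discontinuation the odds ratio is 1.00 in both windows.

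**3. Is that split typical?** With q = 0.40 against 0.25, and 5% to 15% transfused by one year:

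| Treatment ends spread over | OR, Week 52 | OR, whole period | Share of log-odds bias left at Week 52 |
|---|---|---|---|
| 0.5 to 2 years | 0.93 | 0.90 to 0.91 | about 70% |
| 0.5 to 3 years | 0.93 | 0.86 to 0.87 | about 51% to 52% |
| 0.5 to 4 years | 0.93 | 0.83 to 0.84 | about 41% to 42% |

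The longer window enlarges the bias but does not create it.

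**4. Which endpoints are exposed?** Only the proportion transfused. "Number of RBC packs per patient-month exposure to study medication" is already scaled by exposure; it needs only a numerator and denominator that share one window. ESA rescue applies to one arm, so no between-arm comparison can be distorted.

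**The case against.** The strongest reply is that 4.4 defines the endpoints and 11.3.4.1 only gives a general counting rule. The first-to-last-dose sentence is written for the total of RBC units. For the proportion transfused, a whole-period window is implied by position and not stated. The SAP does not always repeat windows: missed dialysis sessions are limited to Week 52 in 4.4 and the limit is not restated in 11.3.3. This stands as a limit on how firmly the conflict can be put.

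It does not settle the matter. SAP 11.3.2 does write Week 52 into the hospitalization analysis, so silence in 11.3.4 is not a consistent convention. The opening line of SAP 11.3 points to the endpoints of section 4.3, not 4.4.

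The second reply is that the transfusion comparison that carries weight is elsewhere. Time to first RBC transfusion is in the fixed sequence (SAP Table 5, non-inferiority margin 1.8), and the time-at-risk formulas in 11.3.4.1 censor untransfused subjects at last dose. That is right, and it confines the point to additional endpoints without multiplicity control.

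A reader might infer that the proportion transfused nearly doubles under 11.3.4. The documents give no rates from which to derive that; under a constant hazard and fixed duration it needs about two years of treatment per subject. A reader might also infer that the odds ratio is biased as planned. That requires treatment length to differ by arm, which is possible but not documented.

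**Conclusion.** The inconsistency is real and worth correcting, with limited consequences. SAP 4.4 and 11.3.4.1 can yield different transfusion proportions, by a factor of about 1.2 to 2.9 under assumed constant hazards and the exposure patterns above. The unadjusted odds ratio departs from 1 only if discontinuation differs by arm. In the worked example it is 0.95 to Week 52 and 0.87 over the whole period.

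It would be too strong to say that the Week 52 limit keeps most of the bias out in general: about 38% of the log-odds bias remains in the worked example and about 41% to 70% in the wider set, because subjects also stop before Week 52.

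For ESA rescue the fault is a mismatch of measure as well as window: 4.4 names a proportion on one ATC code, and 11.3.4.2 derives ESA-weeks on four. That summary is descriptive and roxadustat-only. The primary result and the fixed sequence are unaffected.

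**What to change.** - **SAP 11.3.4.1:** count transfusions and RBC packs from Day 1 to Week 52, or to last dose if earlier, for both endpoints. Use the same person-time as the denominator of packs per patient-month.
- **SAP 11.3.4.2:** summarise the proportion of roxadustat subjects with ESA rescue to Week 52, as 4.4 defines it.
- **Whole treatment period:** report use only as events per patient-exposure-year, alongside the existing time-to-first-transfusion analysis.

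The cost is SAP wording, and it should be settled before results by arm are tabulated. The downside is that transfusions after Week 52 leave the tested proportion. They stay in the whole-period rate, and first transfusions stay in the time-to-event endpoint. The Week 52 proportion still counts early stoppers as untransfused, so it should be read beside that time-to-event result.

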11.3.4.2 ESA Usage as Rescue Therapy for roxadustat-treated Subjects

For roxadustat-treated subjects, ESA, as rescue therapy will be recorded in the ESA log of the eCRF. The total number of ESA-week dose per subject will be calculated.

For each entry that meets the criteria below the ESA-week will be calculated as follows:

- If drug is epoetin alfa, epoetin beta, or an epoetin biosimilar (ATC code: B03XA01), then $\text{ESA-Weeks} = (\text{stop date} - \text{start date} + 1) / 7$;
- If drug is darbepoetin SQ or IV dose (ATC code: B03XA02), then $\text{ESA-Weeks} = 2 \times (\text{stop date} - \text{start date} + 1) / 7$;
- If drug is Mircera IV or SQ dose (ATC code: B03XA03), then $\text{ESA-Weeks} = 4 \times (\text{stop date} - \text{start date} + 1) / 7$;
- If drug is peginesatide dose IV or SQ (ATC cod: B03XA04), then $\text{ESA-Weeks} = 4 \times (\text{stop date} - \text{start date} + 1) / 7$.

The total number of ESA-week during the treatment period is calculated for each subject by the sum of the ESA-week between the analysis date of First dose and the analysis date of Last dose.

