#### 3.6.3.2 Erythropoiesis Stimulating Agents (Roxadustat Arm Only):

The use of ESAs is not permitted during the Treatment Period, except if all of the following criteria are met:

- A subject's Hb level has not responded adequately despite two or more consecutive roxadustat dose increases or the roxadustat dose has reached the maximum dose limit
- Other causes for lack of response or declining Hb, such as iron deficiency, bleeding, acute inflammatory conditions, have been ruled out
- Reducing risk of alloimmunization in transplant eligible patients is a goal.

Roxadustat and ESA may not be co-administered. Treatment with an approved ESA may be initiated  $\geq$  3 days after the last roxadustat dose.

If the situation permits, the Investigator should inform the Medical Monitor prior to initiation of ESA therapy.

Subjects may receive **one course** of ESA rescue during the Treatment Period.

Erythropoiesis-stimulating agent rescue should stop after 4 weeks or once Hb exceeds 9 g/dL, whichever occurs first. If a subject requires more than 4 weeks of ESA rescue therapy due to inadequate Hb response, the Medical Monitor should be contacted.

Treatment with roxadustat may resume after the following intervals:

- Two days after stopping epoetin alfa
- One week after stopping darbepoetin alfa
- Two weeks after stopping methoxy polyethylene glycol-epoetin beta (Mircera®)

If more than one course of ESA rescue is required during the Treatment Period, the subject must be discontinued permanently from the study, and is considered a Treatment Failure.

Inadvertent ESA administration including ESA administration by hospital staff in Roxadustat subjects should not be counted as rescue unless above criteria are met; these subjects may be allowed to continue on study, if considered safe by the Investigator and Medical Monitor.

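### SAP 11.3.4.2 multiplies the calendar length of long-acting ESA rescue by 2 or 4, so summed ESA-weeks are not weeks of ESA and are not on one scale

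*SAP*

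**What the plan says.** SAP 11.3.4.2 deals with ESA given as rescue in the roxadustat arm. Its target is a per-subject total: "The total number of ESA-week dose per subject will be calculated". The unit of calculation is the log entry: "For each entry that meets the criteria below the ESA-week will be calculated as follows". There are four product branches:

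- "If drug is epoetin alfa, epoetin beta, or an epoetin biosimilar (ATC code: B03XA01), then" ESA-weeks are (stop − start + 1)/7.
- "If drug is darbepoetin SQ or IV dose (ATC code: B03XA02), then" the same expression is multiplied by 2.
- "If drug is Mircera IV or SQ dose (ATC code: B03XA03), then" it is multiplied by 4.
- "If drug is peginesatide dose IV or SQ (ATC cod: B03XA04), then" it is again multiplied by 4.

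The entries are then added: "The total number of ESA-week during the treatment period is calculated for each subject by the sum of the ESA-week", taken between first and last dose. The section does not define an ESA-week, does not explain the factors 2 and 4, and does not say whether an entry is a single injection or a course.

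Protocol 3.6.3.2 describes the rescue course being measured: "Erythropoiesis-stimulating agent rescue should stop after 4 weeks or once Hb exceeds 9 g/dL, whichever occurs first". It sets intervals for restarting roxadustat after darbepoetin and after Mircera, so at least two of the multiplied branches can be expected to be used.

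**The concern.** The epoetin branch makes the unit a calendar week. The other branches start from the same calendar duration and scale it up, so equal periods of ESA treatment receive different values according to the product given. A subject's total may mix products, and the arm's summary will.

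What is at stake is how far a reader can judge the roxadustat arm's reliance on ESA. The other planned rescue summaries count subjects: SAP 4.4 lists the proportion needing ESA rescue, citing only the ATC code that 11.3.4.2 assigns to epoetins, and SAP 10 tabulates numbers and proportions of subjects by medication. Only 11.3.4.2 tries to say how much ESA was given. That matters because the US primary analysis (SAP 11.1.2) leaves Hb values affected by rescue in place, so a reader of this open-label non-inferiority comparison will want to know how much ESA lies behind the roxadustat Hb values.

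**Working it through.** The plan states no numeric ESA-week result, so there is nothing to reproduce. The check is to evaluate its own formula.

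**Inputs.** From SAP 11.3.4.2: ESA-weeks = k × d/7, where d = stop − start + 1 in days and k = 1 (epoetins), 2 (darbepoetin), 4 (Mircera, peginesatide). From Protocol 3.6.3.2: a rescue course of 4 weeks, d = 28. For an entry that is a single injection, start = stop and d = 1.

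| Product | k | One-day entry, k × 1/7 | 28-day entry, k × 28/7 |
|---|---|---|---|
| Epoetins | 1 | 0.14 | 4 |
| Darbepoetin | 2 | 0.29 | 8 |
| Mircera, peginesatide | 4 | 0.57 | 16 |

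**Does any reading of the unit make the multiplied branches right?**

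1. *Calendar weeks, as in the epoetin branch.* A 28-day entry should be 28/7 = 4 for every product. The long-acting branches give 2 and 4 times that.
2. *Weeks of cover, with k as weeks per injection.* This is an assumption. One injection should then give k weeks, but a one-day entry gives k/7, one seventh of it. Setting k × d/7 = k gives d = 7, so the formula works only if every injection is logged with a 7-day span. Nothing in the SAP says so.

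**Dependence on logging.** Take two Mircera injections, on day 1 and day 29. As two one-day entries they give 2 × 4/7 = 1.14. As one entry they give 4 × 29/7 = 16.57. The ratio is 16.57/1.14 = 14.5 for the same treatment. Calendar time from first to last injection is 29/7 = 4.14 weeks.

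**Can 2 and 4 simply be moved to the dose count?** Exclusion criterion 1 (Protocol 4.2) limits prior effective ESA use to 3 weeks, and its dosing guidance allows up to 3 IV or 2 SC darbepoetin doses, or 2 CERA doses. At 2 weeks per dose the darbepoetin allowances would be 3 × 2 = 6 and 2 × 2 = 4 weeks. At 4 weeks per dose the CERA allowance would be 2 × 4 = 8 weeks (assuming the Mircera factor applies to CERA; the documents do not equate them). All exceed 3. If the guidance is meant to fit the limit, it implies at most 3/3 = 1 week per IV darbepoetin dose and 3/2 = 1.5 weeks per SC darbepoetin or CERA dose. The restart intervals in Protocol 3.6.3.2, one week after darbepoetin and two after Mircera, do not equal 2 and 4 weeks either.

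**The case against.** The best defence is that ESA-week is never defined. The section introduces the quantity as a dose-like total, so it might be a product-weighted index, and then no figure in the plan is shown to be false. Moreover, the overstatement rests on the calendar reading, the understatement on the weeks-of-cover reading, and both on a log the documents do not show. The quantity has no test, comparison or threshold, and SAP 4.4 does not list it. The number of roxadustat subjects needing ESA can be read without it.

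Much of this stands. It limits the consequence and rules out any single figure for the error. It does not rescue the formula. No weighting is described, a weighted index could not be called weeks, and neither available reading of weeks fits the long-acting branches.

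A reader might infer three stronger things that the documents do not support:

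- *That the factors are weeks of cover per dose, so single injections are understated 7-fold.* The wording of the branches suggests it, but no section says it, and exclusion criterion 1 points to shorter cover.
- *That long-acting courses will be recorded as breaches of the 4-week rescue period.* Neither the SAP nor the protocol compares ESA-weeks with that period, the major-deviation criteria in SAP Table 2 do not use it, and the protocol foresees longer rescue with Medical Monitor contact.
- *That efficacy results are affected.* The responder rule (SAP 4.1) and the rescue-censored repeat of the US analysis (SAP 11.1.2) do not use ESA-weeks.

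**Conclusion.** The point holds as a fault in a derived variable. Followed as written, SAP 11.3.4.2 gives 4, 8 or 16 weeks for the same 28 days and 0.14, 0.29 or 0.57 for the same single day, then adds these values. The result is neither calendar duration nor weeks of cover, and it is not comparable across products. This goes beyond a missing definition, because neither reading makes the multiplied branches correct.

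Its reach is narrow. The variable is descriptive and confined to the roxadustat arm, and no primary, secondary or censoring result depends on it. Epoetin course entries are correct calendar weeks, although single-day epoetin entries still give only 0.14 each. Whether the reported total comes out too high or too low depends on how the ESA log is kept and on which products were used, neither of which the documents show. It deserves correction because it is the only summary in the two documents of the amount of ESA rescue behind Hb values that the US primary analysis leaves uncensored.

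**What to change.** In SAP 11.3.4.2, remove the factors 2 and 4 from the duration formula. Report ESA rescue duration as calendar time for every product, from the first to the last ESA date of each rescue course, with overlapping days counted once, by product and overall. State whether a log entry is an injection or a course, and how entries are joined into a course. This uses only the start and stop dates the SAP already relies on.

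If a weeks-of-cover measure is also wanted, make it a separate variable applied to the number of doses, provided the log records them; the SAP does not show that it does. The sponsor should justify the per-dose factors and reconcile them with the prior-ESA guidance in exclusion criterion 1. The values 2 and 4 should not be carried over by default.

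The cost is a small SAP text and programming change, with no effect on patient care. The drawback is that calendar time does not capture the longer action of long-acting agents.
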